#### **Part A: Single Dose Escalation in Healthy Participants (Crossover)**

In Part A, single ascending doses of GSK3923868 will be assessed in two sequential crossover cohorts (Cohorts 1 and 2) of healthy participants, each with up to three treatment periods. In each cohort, 12 participants will be randomised to one of four treatment sequences. Across the three treatment periods, 9 participants will receive placebo in one of the periods, whereas 3 participants will receive an active dose in all periods (see [Table 2](#) for further details).

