## 6.1. Study Intervention(s) Administered

ARM Name	Cohort 1	Cohort 2	Cohort 3,4	Cohort 5	Cohorts 1-5
Intervention Name	GSK3923868 Capsules for Inhalation	GSK3923868 Capsules for Inhalation	GSK3923868 Capsules for Inhalation	GSK3923868 Capsules for Inhalation	Placebo to match GSK3923868 Capsules for Inhalation
Type	Drug	Drug	Drug	Drug	Placebo
Dose Formulation	Capsule containing Inhalation powder blend Delivered via Monodose RS01 device	Capsule containing Inhalation powder blend Delivered via Monodose RS01 device	Capsule containing Inhalation powder blend Delivered via Monodose RS01 device	Capsule containing Inhalation powder blend Delivered via Monodose RS01 device	Capsule containing Inhalation powder blend Delivered via Monodose RS01 device
Unit Dose Strength(s)	50 mcg	500 mcg	500 mcg	500 mcg	N/A
Dosage Level(s)	50 mcg: one capsule, single dose 100 mcg: two capsules, single dose 250 mcg: five capsules, single dose	500 mcg: one capsule, single dose 1000 mcg: two capsules, single dose 3000 mcg: six capsules, single dose	Planned dose: 3000 mcg: six capsules, daily for 14 days	Planned dose: 3000 mcg: six capsules, daily for 7 days	Number of capsules to match active treatment
Route of Administration	Inhalation	Inhalation	Inhalation	Inhalation	Inhalation
Use	Experimental	Experimental	Experimental	Experimental	Placebo
IMP and NIMP	IMP	IMP	IMP	IMP	IMP
Sourcing	Provided centrally by the Sponsor	Provided centrally by the Sponsor	Provided centrally by the Sponsor	Provided centrally by the Sponsor	Provided centrally by the Sponsor

ARM Name	Cohort 1	Cohort 2	Cohort 3,4	Cohort 5	Cohorts 1-5

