4.3.2.1. Dose Proportionality

The following pharmacokinetic statistical analyses will only be performed if sufficient data are available (i.e. if more than 5 subjects have well defined plasma profiles). If the dose with limited data is at the lower end of the dose range, the data will be excluded and the appropriate analysis conducted on the rest of the data. However if there are non-calculable PK parameter data at intermittent doses no statistical analyses will be performed. A minimum of 3 doses will be required to assess dose proportionality. The assessment of dose proportionality will utilise Part A data only.

Dose proportionality will be assessed using the following two methods:

Pharmacokinetic Statistical Analyses for Dose Proportionality: Power Method	
Endpoint(s)	
• AUC(0-Inf) (if determined, otherwise use AUC(0-t)), Cmax	• Each endpoint to be assessed separately.
Model Specification	
• $\log_e(Y) = \beta \times \log_e(\text{dose}) + \log_e(\alpha)$ where Y is the pharmacokinetic parameter and $\log_e(\alpha)$ is an intercept term.	
Model Results Presentation	
• The coefficient of the slope with 90% confidence intervals, on the log scale, will be calculated, using the pooled estimate of variance, and used to assess dose proportionality.	• Point estimates and confidence intervals for the slope will be reported to 2 decimal places

Pharmacokinetic Statistical Analyses for Dose Proportionality: ANOVA Method	
Endpoint(s)	
• AUC(0-Inf) (if determined, otherwise use AUC(0-t')), Cmax	• Each endpoint to be assessed separately.
Model Specification	
• The PK parameter will be dose-normalised prior to loge-transformation by multiplying by reference dose / dose	• Dose will be fitted as a fixed effect, subject as a random effect using DDFM=KR.
• Separate lines will be fitted for each cohort by including terms for cohort and cohort*log _e (dose). If the slopes are not significantly (p-value<0.05) different from each other, the interaction term will be removed and a single slope estimate obtained. If the slopes are significantly different from each other, a separate slope estimate and associated 90% confidence interval will be reported for each cohort.	• The reference dose will be chosen based on the lowest clinically relevant dose over which PK can be adequately described, with each other dose as the test doses in the construction of the ratio $\mu(\text{test})/\mu(\text{reference})$.
Model Results Presentation	

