5. SAMPLE SIZE DETERMINATION

No formal statistical techniques were used to calculate the sample size for this study.

The number of participants included is deemed an adequate number to provide an assessment of safety and tolerability and pharmacokinetics measurements, and thereby to allow progression to larger clinical studies.

A minimum of 5 participants receiving each dose of active drug (either as a single or repeat dose) are required for the dose escalation meetings. With 5 participants, if the true adverse outcome rate is 5%, the chance of not observing any adverse events at a given dose is 77%. If the true adverse outcome rate is 20%, the chance of not observing any adverse events at a given dose level is 33%.

For Part A, sufficient healthy adult participants will be screened to ensure a total of 12 participants per cohort are randomized with the aim to achieve approximately 12 per cohort completed.

In total for Part A, 9 participants are planned to receive each dose of active drug in each period. If the true adverse outcome rate is 5%, the chance of not observing any adverse events at a given dose is 63%. If the true adverse outcome rate is 20%, the chance of not observing any adverse events at a given dose level is 13%.

In Part B, sufficient healthy adult participants will be screened to ensure 8 participants are randomized to each of the two cohorts, with the aim to achieve approximately 8 completed in each cohort.

For Part C, sufficient participants with asthma will be screened to ensure 16 participants are randomised, with the aim to achieve 16 completers. Part C will be randomised according to two strata, SABA and/or intermittent ICS/LABA users and ICS or ICS/LABA users.

[figure not shown]
In Parts B and C, 12 participants are planned to receive each dose of active drug. The corresponding probabilities for 12 participants with true event rates of 5% and 20% are 54% and 7%, respectively.

This level of predictivity is deemed adequate within this phase of development.

CCI

CCI

For Parts A, B and C if participants prematurely discontinue in the study, they will be replaced at the discretion of the sponsor Medical Monitor in consultation with the Principal Investigator.

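### A p<0.05 test decides whether the separate Cohort 1 and Cohort 2 dose-proportionality slopes are reported; both slopes and their difference should always be shown with 90% CIs

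*SAP*

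**What the plan says.** SAP 4.3.2.1 assesses dose proportionality in Part A by two methods, a power model and an ANOVA on dose-normalised parameters, for AUC and Cmax separately. Terms for cohort and for cohort by log dose are added so that each cohort has its own line. The reporting then branches on a significance test:

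- When the test does not reach the cut-off: "If the slopes are not significantly (p-value<0.05) different from each other, the interaction term will be removed and a single slope estimate obtained".
- Only when the test does reach it is the reader given more detail, namely that "a separate slope estimate and associated 90% confidence interval will be reported for each cohort".

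No margin is set for a slope difference that would matter, no confidence interval for the difference is planned, and no power is given for the test. The rule stands among the bullets for the ANOVA method, although slopes on log dose belong to the power model.

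The design comes from Protocol 6.1 and 4.1 and SAP 5. Cohort 1 receives "50 mcg: one capsule, single dose 100 mcg: two capsules, single dose 250 mcg: five capsules, single dose"; Cohort 2 receives "500 mcg: one capsule, single dose 1000 mcg: two capsules, single dose 3000 mcg: six capsules, single dose". "In each cohort, 12 participants will be randomised to one of four treatment sequences", and "9 participants are planned to receive each dose of active drug in each period".

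Two other outputs do not depend on the test. The ANOVA method presents and plots the ratio of each dose to one reference dose with a 90% CI, and SAP 4.1.1 has Part A outputs summarised by dose level.

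**The concern.** A non-significant interaction shows only that the data did not separate the two slopes at the 5% level. How much that says about their similarity depends on the precision of the comparison. Here the comparison is between different participants, and each cohort covers a narrow dose range: 5-fold in Cohort 1 and 6-fold in Cohort 2.

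If exposure is proportional up to 250 mcg but more than proportional from 500 mcg, the rule can lead to one intermediate slope being reported, with nothing beside it to show how far the cohorts may differ. The upper range matters because it includes 3000 mcg, the planned dose for Parts B and C. The study is otherwise descriptive and tests no formal hypotheses, yet here a hypothesis test decides which estimates the reader sees.

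**Working it through.** **The plan's own figures.** The only design figures are the chances of seeing no adverse event, (1−p)^n. For n=9: 0.95^9 = 0.630 and 0.80^9 = 0.134, which agree with the stated 63% and 13%. The n=5 and n=12 figures also reproduce (77/33% and 54/7%). None of them concerns the slope test.

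**Inputs from the documents.** Doses 50, 100, 250 and 500, 1000, 3000 mcg; 12 participants per cohort in four sequences of three; 9 active profiles per dose, so 6 × 9 = 54 profiles from 24 participants; cut-off 0.05.

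**Assumptions.** Test two-sided; between-participant SD 0.4 on the log scale; within-participant CV 20–50%, with σ = √ln(1+CV²) = 0.198, 0.294, 0.385, 0.472; every profile evaluable; participant as a random effect; the cohort term kept when the interaction is dropped.

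**Effect sizes.** An F-fold departure from proportionality over 500–3000 mcg is a slope difference of ln F / ln 6. For F=1.5 this is 0.405/1.792 = 0.226 (slopes 1.0 and 1.23). For F=2 it is 0.693/1.792 = 0.387.

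**Precision.** Generalised least squares on the actual sequences gives, at CV 30%, slope SEs of 0.092 (Cohort 1) and 0.082 (Cohort 2). The SE of the difference is √(0.092² + 0.082²) = 0.123. Across CV 20/30/40/50% it is 0.084/0.123/0.160/0.195.

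**Chance of pooling.** Degrees of freedom are 54 − 24 − 2 = 28, with critical t 2.048. The noncentrality is the slope difference divided by its SE; for F=1.5 at CV 30% it is 0.226/0.123 ≈ 1.83. The noncentral t distribution gives:

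| Within-participant CV | SE of difference | Pooled, 1.5-fold | Pooled, 2-fold |
|---|---|---|---|
| 20% | 0.084 | 26% | 1% |
| 30% | 0.123 | 57% | 14% |
| 40% | 0.160 | 72% | 36% |
| 50% | 0.195 | 80% | 52% |

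A separate simulation with a random-intercept REML model gave 26/59/72/80% and 1/13/36/53%.

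**If low-dose data are lost.** SAP 4.3.2.1 drops a dose at the low end when its data are limited. Without 50 mcg, power for a slope difference of 0.25 (1.57-fold) falls from 82/50/33% to 44/24/17% at CV 20/30/40% (between-participant CV 40%).

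**What the pooled slope shows.** Inverse-variance weighting gives Cohort 2 a weight of (1/0.082²) / (1/0.082² + 1/0.092²) ≈ 0.56. With true slopes 1.0 and 1.226 the pooled slope averages 1 + 0.56 × 0.226 ≈ 1.13, so roughly half of the Cohort 2 departure remains.

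**What the per-dose ratios show.** At CV 30% the SE of the log ratio is 0.148 for 3000 v 500 mcg, which is within Cohort 2, but 0.219 for 3000 v 50 mcg, which is between cohorts. Suppose Cohort 1 is proportional, the 1.5-fold excess arises over 500–3000 mcg, and 50 mcg is the reference. Then ln 1.5/0.219 = 1.85, and the chance that the 90% CI for 3000 v 50 includes 1 is about Φ(1.70 − 1.85) = 0.44.

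**The case against.** The strongest reply is that the slope is not the only evidence. The ANOVA ratios with 90% CIs and the by-dose summaries appear whatever the interaction test shows. A reader might infer that the rule usually averages a relevant change away, and the documents do not support that. How often pooling happens depends on a CV and a relevance threshold that they do not give. A 1.5-fold change is detected in about three trials in four at CV 20%, and a 2-fold change in most trials below CV 50% if all profiles are evaluable. When pooling does occur, about half the departure remains visible.

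A reader might also infer that the SAP takes non-significance as proof of equal slopes. It does not say so; it describes a model-reduction step. Nor is the pooled slope stated to feed a dose decision. The aim of informing doses in future studies is attached to the in-stream PK analysis (SAP 4.6.2), which is reported separately. Within this study, escalation uses observed and predicted Cmax and AUC, and exposure at the dose used in Parts B and C is measured directly.

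All of that stands and limits the point. It does not remove it. The ratios are taken against one reference, described as the lowest clinically relevant dose with adequate PK, so 3000 v 500 mcg is a planned contrast only if that dose is 500 mcg. With a Cohort 1 reference the comparison with 3000 mcg is between participants and less precise. Neither output gives the slope difference or its uncertainty.

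**Conclusion.** The concern holds as a reporting weakness. A 5% test with no margin and no interval decides whether cohort-specific slopes are shown. Under the stated assumptions it would pool a 1.5-fold departure over 500–3000 mcg in about 26% to 80% of trials as within-participant CV rises from 20% to 50%, and a 2-fold departure in about 1% to 52%. The single slope then dilutes the Cohort 2 departure to roughly half. The ungated per-dose outputs carry part of the evidence but do not replace the missing estimate.

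The percentages rest on assumed variances, complete data and a retained cohort term; the structure of the rule does not. Because this is a secondary, descriptive PK analysis, the change is a cheap improvement of modest priority.

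**What to change.** In SAP 4.3.2.1, remove the p<0.05 condition on reporting. For AUC and Cmax, always report from the power model with a random participant effect and the cohort by log-dose interaction:

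- the slope for each cohort with its 90% CI;
- the difference in slopes with its 90% CI;
- the pooled slope beside them, labelled as a summary.

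Add a sentence that a non-significant interaction is not read as evidence of equal slopes. Move the rule to the power-model table and say whether the cohort term stays in the pooled model. Under the ANOVA method, dose as a six-level factor already accounts for cohort and for cohort by log dose, so the test cannot be fitted there.

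The cost is a short SAP edit and three extra rows per endpoint, with no new data. The cohort-specific intervals will be wider: at CV 30%, with t = 1.70, the half-width is about 1.70 × 0.082 = 0.14 for the Cohort 2 slope and 1.70 × 0.123 = 0.21 for the difference, against about 0.10 for the pooled slope. That width shows what 9 profiles per dose can support.

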**Table 1 Summary of study duration for study Parts A, B and C**

Part	Screening	Treatment Period	Washout Period	Follow-Up	Total Duration
A	Up to 30 days before the first dose.	Cohort 1 will be comprised of three treatment periods (3 days each) with a follow up phone call at 48 hours after each dose.	Will be at least 10 days between doses for each participant.	Between 7 to 14 days following the final dose.	Approx. 11 weeks
A		Cohort 2 will be comprised of three treatment periods (4 days each).			
B		Each participant will receive up to 14 days of treatment with additional observation up to 96 hours after their final dose.	N/A		Approx. 9 weeks
C		Each participant will receive up to 7 days of treatment.	N/A		Approx. 8 weeks

Each participant may only be randomised to one cohort and may only participate in one part of the study.

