4.1.4. Model Checking Diagnostics

Model checking diagnostics for dose proportionality and dose accumulation analysis will include the following:

- The Kenward and Roger method for approximating the denominator degrees of freedom and correcting for bias in the estimated variance-covariance of the fixed effects will be used.
- An unstructured covariance structure for the R matrix will be used by specifying 'type=UN' on the REPEATED line.
 - In the event that this model fails to converge, alternative correlation structures may be considered such as CSH or CS.
 - Akaike's Information Criteria (AIC) will be used to assist with the selection of covariance structure.
- Distributional assumptions underlying the model used for analysis will be examined by obtaining a normal probability plot of the residuals and a plot of the residuals versus the fitted values (i.e. checking the normality assumption and constant variance assumption of the model respectively) to gain confidence that the model assumptions are reasonable.

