4.3. Secondary Endpoints Analyses

All pharmacokinetic analyses will be performed on the Pharmacokinetic Analysis Set. For PK endpoints, all analysis will be performed by Part i.e. Part A (Cohorts 1 and 2 combined), Part B (Cohorts 3 and 4 combined) and Part C (Cohort 5).

Derived pharmacokinetic parameters as data permit, including (but not limited to):

Part A, Cohorts 1 & 2:

- Area under the plasma GSK3923868 concentration versus time curve from time zero to last quantifiable concentration (AUC(0-t)) and from time zero to infinity (AUC(0-∞)) (if determined).
- Maximum observed GSK3923868 plasma concentration (C_{max}).
- Time to maximum observed plasma drug concentration (T_{max}).

Part B, Cohorts 3 & 4:

- AUC(0-□) on Day 1 and Day 14 ($\square=24h$ for once a day dosing regimen) (if determined).
- Cmax and Tmax on Day 1 and Day 14.

Part C, Cohort 5:

- AUC(0-□) on Day 1 and Day 7 ($\square=24h$ for once a day dosing regimen) (if determined).
- Cmax and Tmax on Day 1 and Day 7.

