• Point estimates for the adjusted means on the log _e scale, the mean difference between each dose (test) and the reference dose and associated 90% confidence interval will be constructed using the residual variance. These will not be presented.	• The point estimate and confidence interval will then be exponentially back-transformed to allow the presentation of the adjusted (least square) geometric means for each treatment

Pharmacokinetic Statistical Analyses for Dose Proportionality: ANOVA Method	
	(dose), and point estimates and associated 90% confidence intervals for the ratio test/reference.
•	Point estimates and 90% confidence intervals for AUC, Cmax will be reported to 2 decimal places. Treatment ratios and 90% CIs will be plotted by dose.
•	Plots will also be provided showing the adjusted geometric mean ratio of test to reference treatment (dose) for AUC(0-∞) or AUC(0-t'), and Cmax together with 90% confidence interval.

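### The 90% CI rule for the dose-proportionality ratios (SAP 4.3.2.1, ANOVA method) conflicts with the SAP's own mixed model and, followed literally, makes the cross-cohort intervals too narrow

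*SAP*

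**What the plan says.** SAP 4.3.2.1 assesses dose proportionality in Part A by a power model and by an ANOVA on dose-normalised, log-transformed AUC and Cmax. For the ANOVA the specification reads: "Dose will be fitted as a fixed effect, subject as a random effect using DDFM=KR". Every other dose is compared with one reference dose, which is to be chosen later. Under the presentation of results, the SAP says of each difference that the "associated 90% confidence interval will be constructed using the residual variance". The back-transformed ratios and intervals are then tabulated and plotted. The sentence applies to every test dose and makes no distinction between comparisons within and across cohorts.

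SAP 4.1.4, which names the dose-proportionality analysis, says Kenward-Roger will be used for approximating the degrees of freedom and for "correcting for bias in the estimated variance-covariance of the fixed effects". It adds: "An unstructured covariance structure for the R matrix will be used".

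On the design, Protocol 6.1 gives Cohort 1 the doses 50, 100 and 250 mcg and Cohort 2 the doses 500, 1000 and 3000 mcg. Protocol Table 1 adds: "Each participant may only be randomised to one cohort and may only participate in one part of the study". SAP 4.3 combines the two cohorts for the Part A PK analyses.

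**The concern.** In a model with a random subject effect, residual variance ordinarily means within-participant variance. That is nearly the right basis for comparing two doses that largely the same people received. It is not the right basis for comparing a Cohort 1 dose with a Cohort 2 dose, because no participant received both and differences between people do not cancel. The missing term is the between-participant variance.

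With all six doses kept and any one of them as reference, two ratios stay within a cohort and three cross. With a Cohort 1 reference, the three that cross are for 500, 1000 and 3000 mcg. At stake is the stated precision of those ratios: an interval that is too short could suggest a departure from proportionality, or a precision, that the data do not support. Two programmers could each follow the SAP, one by the CI sentence and one by the model specification, and report different intervals.

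**Working it through.** **No figure to reproduce.** The documents give no CV, interval width or precision target for dose proportionality. All SDs below are assumptions on the log scale: b between participants, w within.

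**Layout** (Protocol Table 2, repeated in SAP 1.2). There are 12 participants per cohort in four sequences of three, hence 24 participants, 54 active observations and 9 per dose. Of the 9 at a given dose, 3 have three active periods and 6 have two. Any two doses in the same cohort share 6 participants (3 of each kind). Doses in different cohorts share none.

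**Formulas.** Model: dose fixed, random participant intercept, independent residuals. Let g2 = b²/(w² + 2b²) and g3 = b²/(w² + 3b²). Generalised least squares gives:

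- cross-cohort variance = 2w² × (9 − 9g2 − 6g3) / [(9 − 3g2)(9 − 12g2 − 9g3)]
- within-cohort variance = 2w² / (9 − 3g2)
- residual-only variance = 2w²/9

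With b = 0 all three equal 2w²/9, as they should.

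**Worked case, b = 0.4 and w = 0.25.**

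- g2 = 0.16/0.3825 = 0.4183; g3 = 0.16/0.5425 = 0.2949.
- Cross-cohort: 0.125 × 3.4657/(7.7451 × 1.3260) = 0.0422, SE 0.205.
- Within-cohort: 0.125/7.7451 = 0.0161, SE 0.127.
- Residual-only: 0.125/9 = 0.0139, SE 0.118.
- The literal interval has 0.118/0.205 = 57% of the proper width. Its coverage is 2Φ(1.645 × 0.574) − 1 = 65%.
- At a true ratio of 1, the 90% interval is about 0.71 to 1.40 from the model and 0.82 to 1.21 from the residual alone.

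**Range of assumptions.**

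| b / w | Cross-cohort SE | Residual-only SE | SE ratio, cross-cohort | Coverage of nominal 90% | SE ratio, within-cohort |
|---|---|---|---|---|---|
| 0 / 0.25 | 0.118 | 0.118 | 1.00 | 90% | 1.00 |
| 0.1 / 0.3 | 0.149 | 0.141 | 1.05 | 88% | 1.02 |
| 0.2 / 0.25 | 0.147 | 0.118 | 1.25 | 81% | 1.05 |
| 0.3 / 0.3 | 0.192 | 0.141 | 1.36 | 77% | 1.06 |
| 0.4 / 0.25 | 0.205 | 0.118 | 1.74 | 65% | 1.08 |
| 0.5 / 0.2 | 0.227 | 0.094 | 2.41 | 50% | 1.09 |

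Coverage uses normal quantiles. Using t on the 26 residual degrees of freedom raises each figure by less than one percentage point.

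**Check with estimated variances.** In 400 simulated REML fits per setting, residual-only coverage was 62% (CVs 40% between, 20% within) and 78% (30%/30%). Model-based coverage was 88.5% and 90.3%. The model-based intervals used an assumed 25 degrees of freedom, not a Kenward-Roger fit.

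**The case against.** The strongest reply is that the SAP already specifies the right model. A standard run with subject random and Kenward-Roger returns a contrast standard error that includes between-participant variance wherever a ratio crosses cohorts. To get the narrow interval, a programmer would have to set that output aside and build the interval by hand from the residual. The CI sentence is also loosely written: grammatically it covers the adjusted means too, and a point estimate cannot be built from a variance.

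Much of this stands. A reader might infer that the SAP uses the residual variance alone and so plans wrong intervals. The documents do not support that: nothing in the sentence excludes the subject component, and the model text points the other way. What does not fall away is the conflict. The CI sentence is the only one that says what this method's intervals are built from. For accumulation, SAP 4.3.2.2 takes the least-squares mean difference and its interval with no such phrase.

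A second reply is that an unstructured R matrix has no single residual variance. If R carries all the covariance and there is no separate subject effect, its diagonal is total variance, and the cross-cohort intervals need not be too narrow. That is correct. But the sentence is then undefined, and a random subject effect on top of an unstructured R is over-parameterised. Either way the text needs an edit.

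Third, SAP 4.3.2.1 allows low doses with limited data to be excluded. If all Cohort 1 doses go, no cross-cohort ratio remains. The plan should still be right for the planned case.

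A reader might also infer that these ratios feed the PK modelling and later dose selection. No section says so. The in-stream PK analysis (Protocol 9.5.2, SAP 4.6.2) and the population PK work (SAP 4.3.2.3) do not cite them, and escalation compares Cmax and AUC with fixed exposure limits (Protocol 4.3.1 and 6.5.1).

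**Conclusion.** The CI sentence in SAP 4.3.2.1 is inconsistent with the model in that section and with SAP 4.1.4. Taken literally, with residual variance read as within-participant variance, it makes the intervals too narrow for cross-cohort ratios whenever between-participant variance is above zero.

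It would be tempting to call the intervals far too narrow throughout. The documents give no variability figures to support that: over the assumed SDs above, the effect runs from small to severe, and ratios within a cohort are barely touched.

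The figures rest on the planned sequences with no dropouts, all six doses analysable, and a random-intercept model with a single residual variance. The correction is of moderate weight. Dose proportionality is a descriptive secondary PK analysis, no formal hypothesis is tested, no proportionality limit is set, and a power model is reported alongside.

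**What to change.** 1. In SAP 4.3.2.1, replace the reference to the residual variance with: *using the Kenward-Roger-adjusted standard error of the contrast from the mixed model, including between-participant variance*.
2. In SAP 4.1.4 and 4.3.2.1, state whether within-participant correlation is modelled by a random subject effect or by the unstructured R matrix, not both.
3. In the tables and plots, footnote each ratio of a Cohort 1 dose to a Cohort 2 dose as a between-participant comparison.

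This needs a few sentences in the SAP and no new data. The cost is wider cross-cohort intervals: by the table above, about 5% wider at 0.1/0.3 and about 2.4 times as wide at 0.5/0.2.
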